# **Administrative Information**

## 1. Title

Title: Saving young lives: Triage and management of sepsis in children using the point-of care Paediatric Rapid Sepsis Trigger (PRST) tool

Lay Title: Development and testing of a digital tool for recognizing sick children

### 2. Protocol Version

Version 5.0, October 19, 2020

### 3. Funding

This study is funded by the Wellcome Trust Innovator Award.

### c. Role of study sponsor and funders

The study sponsor and funders do not have a role in in study design; collection, management, analysis, and interpretation of data; writing of the report; and the decision to submit the report for publication. They will not have ultimate authority over any of these activities.

- d. Collaborating organizations
- 1. The University of British Columbia
- 2. Centre for International Child Health
- 3. Kenya Medical Research Institute (KEMRI)
- 4. Walimu
- 5. Jinja Regional Hospital
- 6. Mbagathi County Hospital
- 7. Kiambu County Referral Hospital

### Introduction

### 5. Background and Rationale

The global burden of pediatric mortality in low- and middle-income countries (LMICs) remains high, with 4.9 million deaths in children under 5 in 2016 [1]. Most of these deaths are due to sepsis, which is defined as the body's response to an infection (such as pneumonia, diarrhea, or malaria) leading to organ damage and ultimately morbidity and mortality [2]. Sepsis is common worldwide, but countries in Africa report substantially higher case fatality rates (adjusted odds ratios: Africa, 7.89 [95% confidence interval (CI), 6.02-10.32]) as compared to the United States [3]. Recognizing the enormity of the global burden of sepsis (death, disability, social, and economic) led to a 2017 World Health Assembly resolution highlighting the need to prioritize prevention, recognition, and early treatment of sepsis [4].

Sepsis disproportionately affects socioeconomically disadvantaged populations in LMICs. Encouragingly, most deaths from sepsis are preventable by early detection and treatment. The majority of deaths occurring in health facilities happen occur as a result of delayed, inadequate, or inappropriate treatment. Every hour of delay in therapy is associated with an escalating risk of morbidity and mortality [5]. Simple, highly effective interventions to treat sepsis, including antimicrobials and intravenous (IV) fluids, are available at care facilities in LMICs. Yet availability and readiness to provide treatment is not always enough [6]—timely treatment may not occur because the sickest children are not prioritized.

The World Health Organization (WHO) advocates the use of Emergency Triage Assessment and Treatment (ETAT) guidelines to triage children in resource limited settings [7]. Although the ETAT system is widely adopted in LMICs, successful implementation of the guidelines into clinical practice is not always the case [8]. In LMICs, patients are frequently admitted and treated on a first-come, first-serve basis, leading to delayed care for children who are in need of

urgent treatment. These priority children can receive faster treatment if every child is rapidly triaged upon arrival to identify danger and priority signs of sepsis [9]. However, sepsis is a syndrome that mimics many conditions and few health workers can confidently triage and diagnose sepsis. Evidence-based trigger tools and protocols may be useful in skilled hands, but require complex decision-making based on physiological, clinical, social, and laboratory parameters.

The purpose of this study is to develop a digital triage tool that can be used rapidly and reliably, without the need for extensive memorization or training, by frontline health workers (including nurses and non-physician clinicians) to identify critically ill children (including those with sepsis). The digital platform consists of a mobile application integrating a pulse oximetry sensor attached to this device, with embedded smart algorithms that predict a critically ill state, or level of risk (below) in a child presenting at the hospital. The platform also includes an interactive dashboard located in strategic locations (e.g., laboratory, consultation rooms), which connects to the mobile application through a secure local network and displays the triage data to provide real-time monitoring for the physicians who manage the patients.

Over the past 10 years, we have developed, implemented, and evaluated the core technology of the Digital Triaging Platform including vital sign measurement devices (PhoneOx [10] and RRate [11]) and the mobile application and dashboard [12][13][14]. We have already identified candidate predictor variables using a modified Delphi process [15], and developed a risk prediction model based on the need for admission using predictors collected in over 1000 children at a Kenyan hospital [16].

### 6. Objectives

**Objective A:** To develop and clinically validate a digital trigger tool and clinical dashboard for improving the hospital wait time to treatment administration in children with severe infections/suspected sepsis.

### **Breakdown**

- 1. To collect a pre-selected list of clinical variables from participants and use the data to develop a prediction model based on the need for hospital admission.
- 2. To develop a digital triage tool by implementing the derived prediction model and triage guidelines used in the study hospitals into the Digital Triaging Platform.
- 3. To evaluate the usability/feasibility of the digital trigger tool prior to implementation in the study hospitals.
- 4. To clinically evaluate effectiveness of the triage tool by comparing hospital wait times to treatment for children before and after implementation of the digital triage tool.

### Additional objectives due to the impact of COVID-19 at the study sites:

1. Develop data driven prediction models for identifying vulnerable children with suspected sepsis that are robust during future COVID-19 surges and novel pandemics.

- 2. Identify the variables that contribute to vulnerability in children with suspected sepsis, during pandemic and non-pandemic times.
- 3. Collect additional COVID-19 related prediction variables to inform understanding of the severity, risk factors, and clinical features of this disease at our three study sites (rural, urban and peri-urban).

**Objective B:** To validate the use of an automated Radio-Frequency Identification (RFID) method to track timeliness of interventions.

RFID tags will be small paper or plastic objects that can be attached to clothing or worn as a bracelet, anklet, or necklace (as preferred by child's caregiver) that use Bluetooth frequency band. The tag sends signals which allows tracking exactly where a patient is at a given time for analysis. For example, if a patient wearing an RFID tag enters a room, a reader in the room will detect the signal and add a timestamp for when patient was in the room. The Bluetooth frequency is no different to that used by mobile phones and is not expected to interfere with other processes in the hospital.

**Objective C:** To conduct an economic evaluation to contextualize our results for informing budgetary decisions of scaling-up Smart Triage.

# 7. Trial Design

This is a pre-post intervention study involving pediatric patients presenting to the study hospitals in seek of medical care for an acute illness. The study involves three phases: (I) Baseline Period, (II) Interphase Period, (III) Intervention Period.

### Changes due to the impact of COVID-19:

Due to the impact of COVID-19 at our study sites, there will be an addition of a pandemic phase during Phase I. This will allow us to explore any differences that exist in a pandemic period compared to a non-pandemic period and develop data driven prediction models for identifying vulnerable children with suspected sepsis that are robust during future COVID-19 surges and novel pandemics.

	Phase I (3 months) Baseline Period: Pandemic Cohort	Phase I (3 months) Baseline Period: Post- Pandemic Cohort	Phase II (1-3 months) Interphase Period	Phase III (5-6 months) Intervention Period	Analysis Period
Site 1:				Routine use of	
Mbagathi				digital triage tool	

County	Data collection	Data	Technology	by hospital	Determine
Hospital,	on predictors	collection on	development	nurses.	effectiveness of
Nairobi	and outcomes	predictors and	and usability		intervention,
	by study nurses.	outcomes by	testing	Data collection	results
		study nurses.		continues as	presentation and
Site 2: Jinja				done in Phase I	dissemination.
Regional				by study nurses.	
Referral					
Hospital,					
Jinja					
Control	Ongoi	ing baseline data	collection (12 n	nonths)	
Site: Kiambu					
County					
Hospital,					
Nairobi					

### Figure 1. Study Schema.

#### Updated Timeline due to COVID-19:

Phase:	Baseline	Training		Intervention	A	nalysis
Duration:	6 months	1 month		6 months	1	l months
Site 1: Kenya	Delayed	Delayed		Delayed	B	aseline data ollection
Site 2: Jinja	Baseline data collection	Model development, usability testin and training	ıg,	Routine use of PRST and continued data collection	St ar re R	tatistical nalysis and porting of esults
Control: Kenya Delayed					B co	aseline data
Additional Site: Gulu Uganda			Base	eline data collectio	n	Routine use of PRST

Phase I (6 months) will be a prospective observational cohort at Mbagathi County Hospital in Nairobi, Kenya, and Jinja Regional Referral Hospital in Jinja, Uganda. During this period, there will be no changes to healthcare delivery procedures in the study hospitals. Triage will continue to be performed by hospital staff using ETAT+ guidelines, the system that is currently in effect at the study hospitals [7]. Data collection will be undertaken in the triage waiting area. While participants are waiting for their turn to be seen by the **hospital triage nurses**, our trained **study nurses** will collect data on a pre-selected list of predictor variables (see Appendix A). These data will be used to develop a clinical prediction model based on the need for hospital admission.

#### Changes due to the impact of COVID-19:

We anticipate that the weekly number of admissions will return to baseline over the next 2-3 months. Therefore, Phase I will be split into baseline data collation during a pandemic period (first 3 months), and non-pandemic period (latter 3 months)

**Control Site (Phase I, 12 months):** Kiambu County Referral Hospital in Nairobi, Kenya will serve as the control site and no intervention will be implemented. At this site, Phase I will commence for a period of 12 months. There will be no Phase II or Phase III.

Phase II (1-3 months) will involve technology development, usability testing, and training.

**Phase IIa: Technology Development.** A risk prediction model will be derived using the data collected in Phase I and implemented in a Digital Triaging Platform, along with a digitized version of the ETAT+ guidelines. The Digital Triaging Platform, including vital sign measurement devices (PhoneOx [10] and RRate [11]) and the mobile application and clinical dashboard [12][13][14] has already been developed and evaluated. Once the digital triage tool has been developed, it will be evaluated in potential users using simulated patient scenarios and a 'Think Aloud' method.

### Phase IIb: Usability Testing and Training.

#### Usability Testing Initiative

The digital triage tool will be evaluated for ease of interface navigation, functionality and basic workflow. A sample of 15 potential users in the study hospitals to represent the primary user groups will be selected for participation in the 60-minute-long usability testing initiatives. Participants will be recruited through word of mouth as there is a very small cadre of potential participants. The objective of the training is to (1) ensure healthcare workers understand how to correctly collect and interpret patient information, and (2) to obtain feedback on the digitization of the tool. Training will use a framework that meets key international norms for testing digital tools, including, the think-aloud method and a questionnaire.

Each training session will be conducted by a moderator and observer. During the evaluation, the observer will be seated next to the participant and will record user interaction with each interface, comments, errors, and duration of each task. Participants will be given 3-5 patient scenarios which will list hypothetical information to be entered into the app (see Appendix B). This information will be designed to represent routine data collected during triage examination at the study hospitals. The moderator will provide the fictional charts to participants and instruct them throughout the tasks. During the simulated patient scenarios, participants will be asked to think aloud, in order to assess their thought process as they used the app. Participants will be specifically instructed to comment on the layout of the app screen, the dialogue on each interface, the order of tasks, and any additional observations or opinions. After learning the basics of the digital platform, the participants will be read the think aloud instructions and asked

to perform the list of tasks and answer questions (see Appendix C). The observer will complete a checklist to ensure that all tasks were completed, questions will be asked to evaluate task comprehension, and notes will be taken about whether help was needed in completing each task. At the end of the training session, participants will complete a triage tool training questionnaire (Appendix D) to provide an understanding of the practical benefits and drawbacks of incorporating the digital triage tool into a clinical context. The questionnaire will utilize open ended questions and comment responses. from this evaluation. Responses from the survey will be anonymous. The data generated from the training phase is fictitious and will not be linked to any individual subject. In light of ongoing physical restrictions due to COVID-19, the sessions will be recorded digitally with multiple audio and video feeds of each usability session. The session will record (1) the participant's screen from within the software using screen capture technology (video only); (2) the participant physically using the digital tool (video only); (3) the participant's reactions and comments towards the digital tool (audio and video).

#### Interviews

After the digital triage tool has undergone usability testing and updates, and has been implemented in the study hospitals, a one-week pilot period will take place. At the end of this period, healthcare workers and hospital staff will be invited to participate in an interview to allow evaluation of the acceptability, usability, and feasibility of the digital triage tool in the context of the hospital. A total of 30 staff, including clinicians, doctors, nurses, and administrators, will be selected to participate in focus group discussions and one-on-one interviews. Interviews will take place after the pilot phase, and periodically throughout the interventional phase (Phase III) to capture experiences and feedback from hospital staff throughout the course of the study. Interviews may be conducted either in person in a private room on site at the hospital, or, in consideration of personal safety and ongoing physical distancing restrictions due to COVID-19, through a secure digital conferencing software. Interviews will last approximately 60 minutes, during which the interviewer will ask the interviewees series of questions from a semi-structured interview guide (Appendix E).

Transcriptions, Think Aloud observations, and interview recordings will be analyzed using the Framework Method [17] to assess attitudes of health workers. Responses will be transcribed and coded using NVivo [18], for the identification, examination and interpretation of emerging themes and patterns. Results from the analysis, feedback from the questionnaires, and comments on the observer checklists will be used to generate a report with suggested improvements to be shared with the quality improvement implementation team prior to Phase III.

**Phase III (3-6 months)** will be an interventional period involving routine use of the digital triage tool by the hospital triage nurses at Mbagathi County Hospital in Nairobi, Kenya, and Jinja Regional Referral Hospital in Jinja, Uganda. The digital triage tool will not replace triage policies already in place at the study hospitals, but rather it will supplement and strengthen existing triage systems. As done in Phase I, **study nurses** will collect data on the pre-selected list of predictor variables in the triage waiting area while participants are waiting to be seen by **the** 

**hospital triage nurses** (who will be using the digital triage tool). Continued collection of predictor variables will allow comparison of participant characteristics in the pre-intervention cohort and the post-intervention cohort.

# Methods: Participants, Interventions, and Outcomes

# 8. Study Setting

### Involved in Phase I, Phase II, and Phase III:

1. Experimental Site #1: Jinja Regional Referral Hospital in Jinja, Uganda

Jinja, a city of approximately 90,000 people, is located in the Eastern region of Uganda. The Jinja Regional Referral Hospital pediatrics ward admits approximately 5000 patients per year and the outpatient department sees approximately 100 patients per day.

2. Experimental Site #2: Mbagathi County Hospital in Nairobi, Kenya

### **Involved in Phase I only:**

3. Control Site: Kiambu County Referral Hospital in Nairobi, Kenya

A typical outpatient department (OPD) in the Kenyan study hospitals serves approximately 20,000 children per year and is staffed by one or two nurses who conduct triage and administer treatment, two or three clinicians who review patients and issue prescriptions, and one additional nurse who administers treatment and provides counselling to caregivers of children. The hospitals admit approximately 2,000 pediatric patients per year.

### Changes due to COVID-19

The global COVID-19 has introduced many challenges to the successful completion of this project. We have been unable to initiate Phase I of the project in Nairobi, Kenya due to restrictions implemented to reduce the risk of spread of COVID-19. We have made good progress in recruitment in Jinja, Uganda. I consultation with our investigators, implementation partners and funders we have decided to add an additional site at Gulu Regional Hospital in Uganda. Gulu Regional Referral Hospital will serve as a control site while the intervention phase (Phase III) takes place at Jinja Regional Referral Hospital. Once the intervention period has been completed in Jinja, the intervention will be introduced at Gulu Regional Referral Hospital.

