#### **Outcomes Analysis**

We will compare the proportion of children at the two intervention sites receiving a completed bundle within 60 minutes to the historical and the contemporaneous control group (Marascuillo procedure). The median time to an appropriate bundle of care will be compared using a Mann–Whitney U test. The triage prioritization between the phases and the proportion of children who received and appropriate bundle of care within each triage categorization will be compared with Fisher's exact tests. Segmented regression analysis of the interrupted time series of the pre- and post- intervention periods will be used to assess immediate effects and effects over time, controlling for prior trends that may continue without our intervention. Quantile regression will be used to estimate the median differences. We will compare the estimated times at end of the intervention period with the expected counterfactual value, had the pre-intervention trend continued as if the intervention never occurred. We will compare the time to event (treatment bundle) using the Kaplan-Meier estimator with censure at 180 minutes. Secondary outcomes will be compared using generalized estimating equations.

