#### **Outcomes** analysis

We will be conducting our primary analysis using a difference in differences method. For our primary analysis, a logistic regression model for receipt of bundle of care within 1 h will be fit including: 1) phase of study (pre vs. post PRST) and 2) group (intervention versus control) as independent dummy variables and 3) their interaction. The interaction term corresponds to the difference in log-odds between groups in baseline vs intervention and it's exponent as the ratio of odds ratios. We will summarise this difference by estimating the marginal effect (risk difference) of phase in both the control and intervention groups. The difference of these marginal effects is the so-called 'difference in difference' for a binary outcome [24]. Confidence intervals will be based on the delta-method, or bootstrapping, where appropriate. A similar approach will be used for binary secondary outcomes (mortality, readmission), or quantile regression for median time to bundle of care, a non-parametric outcome.

Subgroup analyses specified a priori include Ugandan vs. Kenyan intervention site, young infant (under 2 months old) vs. children under 5 vs. older children, and presentation during day-shift hours versus night-shift hours (if applicable). We will also perform subgroup analyses on each triage category (emergency, priority, queue); patients from the pre-intervention phase will be retroactively categorized into these subgroups for this analysis. These subgroup analyses will be conducted with the inclusion of a three-way interaction between said variable, phase, and group. Statistical significance will be based on a likelihood ratio test comparing models with and without this term. This three-way interaction term would represent potential interactions between different subgroups and our difference in odds ratio obtained in our primary analysis, and results will again be presented on the risk difference scale based on marginal effects. This method of subgroup analysis sometimes termed a difference in difference in differences method.

Although none are expected, if there are any time varying confounders identified during the study that differ between intervention and control (health system or policy changes, natural events, changes in patient populations etc.) they will be included in above models as sensitivity analyses.

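### Under protocol v5.0 no control hospital is scheduled to collect data in Jinja's baseline, so the only analysis labelled primary (difference-in-differences) cannot be estimated, none is named in its place, and the concurrent-control comparison becomes an unadjusted Jinja-versus-Gulu contrast

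*Combined protocol and SAP*

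**What the plan says.** The material holds two analysis plans. The protocol article (June 2020, Outcomes analysis) states "We will be conducting our primary analysis using a difference in differences method". Its logistic model for receipt of the bundle within one hour contains phase, group and their interaction. Kiambu, observed for 12 months without the tool, was to supply the control data in both periods.

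Protocol v5.0 (October 2020) changes the sites. Section 8, Changes due to COVID-19, reports "We have been unable to initiate Phase I of the project in Nairobi, Kenya due to restrictions" and adds Gulu: "Gulu Regional Referral Hospital will serve as a control site while the intervention phase (Phase III) takes place at Jinja Regional Referral Hospital". Gulu then receives the tool once Jinja's intervention period is over. The updated timeline in section 7 lists both Kenyan sites as delayed. Its row "Additional Site: Gulu Uganda" shows nothing under Baseline, and baseline collection there appears alongside Jinja's intervention period.

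Other v5.0 text keeps the old arrangement. Section 7 still says "Kiambu County Referral Hospital in Nairobi, Kenya will serve as the control site and no intervention will be implemented", and the schema table in section 7 and the site list in section 8 agree with that sentence. Section 17, Outcomes Analysis, compares children "at the two intervention sites receiving a completed bundle within 60 minutes to the historical and the contemporaneous control group (Marascuillo procedure"). It adds Mann–Whitney, Fisher, segmented regression, quantile regression and Kaplan–Meier analyses. It does not mention difference-in-differences and calls none of its analyses primary. Section 11 names primary outcomes, not a primary analysis.

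**The concern.** A difference-in-differences needs the control hospital's rate in both periods. If the control is observed only while Jinja uses the tool, nothing shows how the two hospitals compared beforehand. The article's primary analysis then yields no estimate, and a team that turns to v5.0 finds six or more analyses with none designated. The choice among them could be made after the data are seen.

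The comparison with the contemporaneous control also changes its meaning. Without a control baseline, a difference between Jinja and Gulu mixes any tool effect with whatever already separated the two hospitals, such as staffing, case mix or patient flow. The planned effect is small (20% of 27% is 5.4 points), so a modest standing gap could imitate it or hide it.

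**Working it through.** **Inputs.** Baseline proportion 27% and 750 children per condition (v5.0 section 13); relative change 20%, so 27% to 32.4% (article, Sample size); target of 4,000 per site (v5.0 section 13), from which I assume 2,000 per phase or hospital. The documents give no rate for Gulu, so every hospital gap below is an assumption shown as a range.

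**The plan's own figure.** The usual two-proportion formula at 80% power and alpha 0.05 gives, for 27% to 32.4%, 1,123 per group two-sided or 885 one-sided. For 27% to 21.6% (v5.0 speaks of a decrease) it gives 990 or 779. None equals 750. That is a separate matter. I use 750 here only as the plan's stated number.

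**1. Can the article's model be estimated?** Write the log-odds as a + b·phase + c·group + d·phase·group. The scheduled cells are:

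- Jinja before: a + c
- Jinja during: a + b + c + d
- Gulu concurrent: a + b

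These are three equations in four unknowns (rank 3 of 4). Since d = (Jinja during − Jinja before) − (Gulu during − Gulu before), the missing last term leaves d undetermined. Adding a Gulu-before cell restores rank 4. Gulu's later tool period does not, because Gulu is then treated and v5.0 schedules no Jinja collection after Phase III. Two contrasts remain estimable: Jinja during minus before, and Jinja minus Gulu during Phase III.

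**2. The Jinja-versus-Gulu pair read alone.** With three groups (Jinja before, Jinja during, Gulu) the Marascuillo cut-off is √(chi-square 0.95, 2 df) = 2.448. For a true gap g and no tool effect, SE = √{[0.27 × 0.73 + (0.27 + g)(0.73 − g)]/n}, and the chance of significance is Φ(g/SE − 2.448) + Φ(−g/SE − 2.448). For g = 5 points:

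- n = 750: SE = 0.0235, g/SE = 2.13
- n = 2,000: SE = 0.0144, g/SE = 3.47

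| Assumed gap | 750 per hospital | 2,000 per hospital |
|---|---|---|
| 0 points | 1.4% | 1.4% |
| 2 points | 5.7% | 15.0% |
| 3 points | 12.3% | 36.5% |
| 5 points | 37.4% | 84.7% |

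Which hospital is faster decides whether the error favours the tool.

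**3. Precision of the two within-Jinja options.**

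Plain pre/post: 95% half-width = 1.96 × √(2 × 0.27 × 0.73/n), which is 4.5 points at 750 per phase and 2.8 at 2,000.

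Segmented level change: assume baseline months 0–5, a one-month gap, tool months 7–12, equal monthly numbers and no autocorrelation. Compare the post-period line at month 7 with the baseline line extended to month 7. Each period has a sum of squared month deviations of 17.5.

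- Variance multiplier: (1/6 + 4.5²/17.5) + (1/6 + 2.5²/17.5) = 1.324 + 0.524 = 1.848
- Monthly variance: 0.27 × 0.73/(n/6)
- Half-width: 1.96 × √(1.848 × 0.1971 × 6/n), which is 10.6 points at 750 and 6.5 at 2,000

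Against 5.4 points, two-sided at 5%, power is about 17% and 37% for the segmented level change, and about 63% and 96% for plain pre/post.

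**4. An abrupt change inside the baseline.** Suppose a lasting 5-point step at the pandemic/non-pandemic split and no tool effect. The plain difference is 5 − 2.5 = +2.5. The baseline line has slope 5 × (0.5 + 1.5 + 2.5)/17.5 = 1.286 and reaches 2.5 + 4.5 × 1.286 = 8.3 at month 7. The segmented level change is therefore 5 − 8.3 = −3.3. A purely linear trend biases the segmented estimate by zero.

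**The case against.** The strongest reply is that v5.0 is the later document and has its own analysis section. A team following it would not fit the article's model, so this is a conflict between two documents and not a failed analysis. That is fair as far as it goes, and a reader should not infer that the study can yield no effect estimate: the within-Jinja comparisons remain available. But v5.0 never says that the article's primary is withdrawn, and it labels nothing in its place. Its objective, design, primary outcome and sample size (sections 6, 7, 11 and 13) all lean towards pre/post without designating an analysis.

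A reader might also infer that the whole Marascuillo comparison is biased. It is not. With a standing gap and nothing else changing, the Jinja before/during pair would be null, and the gap would also appear between Jinja before and Gulu. The error rates above describe one pair read alone.

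Nor do the documents prove that Gulu has no data before Jinja's Phase III. Section 8 says when Gulu acts as control, not the day its collection starts, and the timeline table is broken in the text, so a short stretch near the training month cannot be ruled out.

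Finally, it is tempting to insist on segmented regression because v5.0 includes it as "controlling for prior trends that may continue without our intervention". The figures do not support insisting: it is much less precise and, under the assumed step, slightly more biased than plain pre/post. Nor does the protocol predict a step. It says "Phase I will be split into baseline data collation during a pandemic period (first 3 months), and non-pandemic period (latter 3 months"), only hypothesises a change in case mix, and expects admissions to recover over two to three months.

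**Conclusion.** The point holds in limited form. On the v5.0 schedule the control-by-baseline cell is empty, the only analysis labelled primary is not estimable, and v5.0 neither withdraws nor replaces it. The concurrent pair in section 17 cannot separate a standing hospital difference from a tool effect. Its false-significance rate when read alone runs from about 6% (2-point gap, 750 per hospital) to 85% (5-point gap, 2,000), against 1.4% with no gap.

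The identification result rests on the section 7 timeline and the section 8 update taking precedence over the unrevised Kiambu text. The error rates rest on assumed gaps, a 27% rate at one hospital and independent children. The 2,000 figures also assume that half of the site target falls in each phase.

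**What to change.** 1. Reconcile the Kiambu text (section 7 schema and control-site paragraph, section 8 site list), the section 17 wording on two intervention sites and a contemporaneous control, and the article's Outcomes analysis with the v5.0 sites. State Gulu's collection start date. State that the difference-in-differences is withdrawn as primary unless baseline-period control data exist.
2. Do not treat the Jinja-versus-Gulu contrast alone as evidence of effect. Use Gulu's concurrent series as a check on calendar change, and Gulu's own later pre/post comparison as replication.
3. Name one within-Jinja pre/post analysis of the 60-minute proportion as primary. The natural candidate is the comparison that v5.0 sizes in section 13, adjusted for the predictors collected in both phases, with the segmented regression and a pandemic/non-pandemic term as sensitivity analyses. Choosing between plain and segmented is the sponsor's trade-off: the segmented level change removes a linear trend at more than twice the interval width, and neither removes an abrupt change. Whichever is chosen, state its expected precision.

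The cost is wording, on data already planned, plus an openly weaker causal claim because there is no baseline control. If the segmented analysis is made primary, the cost also includes most of the power for a 5.4-point effect.
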